##### 4.9.2 Statistical Hypothesis, Model, and Method of Analysis

A random-coefficient linear mixed-effects model will be fit to all available paroxetine concentration -  $\Delta\text{QTc}$  data pairs, as described in a white paper (Garnet C et al., 2018 [3]). In this model,  $\Delta\text{QTc}$  is the dependent variable and paroxetine concentration and time after dose and baseline are independent variables, it takes the form of:

$$\Delta\text{QTc}_{i,k} = (\theta_0 + \eta_{0,i}) + (\theta_1 + \eta_{1,i}) * C_{i,k} + \theta_{2,k} * \text{TIME}_{i,k} + \theta_3(Q\text{Tc}_{i,k=0} - \overline{Q\text{Tc}_0}) + \varepsilon_{i,k}$$

In this equation:

- $\Delta\text{QTc}_{i,k}$  is the change from baseline in QTc for participant  $i$  at time  $k$ ;
- $\theta_0$  is the population mean intercept in the absence of a treatment effect;
- $\eta_{0,i}$  is the random effect associated with the intercept term  $\theta_0$ ;
- $\theta_1$  is the population mean slope of the assumed linear association between concentration and  $\Delta\text{QTc}_{i,k}$ ;
- $\eta_{1,i}$  is the random effect associated with the slope  $\theta_1$ ;
- $C_{i,k}$  is the concentration for participant  $i$  and time  $k$ ;
- $\theta_{2,k}$  is the fixed multilevel categorical effect associated with time factor. If inspection of the Day -1 data suggests a time-dependent trend, alternative parameterization for the time variable, for example based on (co)sine function such as described in Koch et al 2002, could be used if relevant;
- $\theta_3$  is the fixed effect associated with the difference of each baseline values to the overall mean (Baseline  $\text{QTc}_{i,k=0}$ ,  $\text{QTc}_0$  is overall mean of  $\text{QTc}_{i,k=0}$ , i.e., the mean of all the baseline (= time 0) QTc values).

It is assumed the random effects ( $\eta_{0,i}$  and  $\eta_{1,i}$ ) are normally distributed with mean [0,0] and an unstructured covariance matrix G, whereas the residuals are normally distributed with mean 0 and variance R. In case of the unstructured covariance matrix for random effects is not supported by the data or results in null estimates, and may result in non-convergence problems, other simplified or reduced structures will be investigated (Variance component with 2 random effects, 1 for slope and 1 for intercept, variance component with 1 random effect for intercept or slope).

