The  $\Delta QTc$  and paroxetine concentrations corresponding to all doses (20, 40, and 60mg) will be used for the modelling (Both drawn from each participant at same time intervals). Moreover,  $\Delta QTc$  obtained on Visit 2 (Day -1) after baseline will be included in the model with paroxetine concentrations set to 0. This model assumes a linear correlation between paroxetine plasma concentration and  $\Delta QTc$ . While it is assumed that such a correlation (if at all) can be considered linear at clinically meaningful doses, other parameterizations such as the classical Emax function may be explored if the linear approach is found inappropriate.

The model parameters will be estimated including the precision around the parameter estimates using a maximum likelihood approach.

The following SAS® code will be used for the random-coefficient linear mixed-effects model:

```
PROC MIXED DATA=ADEG (WHERE=(XXXX)) NOITPRINT CL NOCLPRINT METHOD=ML PLOTS=NONE;
ODS OUTPUT SOLUTIONF=SOLF ESTIMATES=ESTF COVPARMS=COV;
CLASS USUBJID ATPTN ;
MODEL CHG=BASEC ATPTN PCSTRESN / DDFM=KR SOLUTION ALPHAP=.05 CL RESIDUAL
OUTPM=PRED OUTP=IPRED;
RANDOM INT PCSTRESN /SUB=USUBJID TYPE=UN;
ESTIMATE "DDQTC_60MG" INT 1 PCSTRESN CMAX60MG /CL ALPHA=.1;
RUN;
```

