#### 4.9.2.3 Summary of measure

Individual Cmax values for participants at the 60 mg dose will be used to calculate the Cmax geometric mean. Based on the estimated model, the calculated geometric mean Cmax for dose 60 mg will be used in the fitted model to predict the upper limit of the 90% CI of  $\Delta QTc$  at dose 60 mg as follows (in the case of a linear model):

$$\overline{\Delta QTc_{60mg}} = \theta_0 + \theta_1 Cmax(60mg)$$

$$90\% CI = \overline{\Delta QTc_{60mg}} \pm t(0.95, DF) \times SE$$

$$SE = \sqrt{var(\theta_0) + C_{max}^2(60 mg) var(\theta_1) + 2C_{max}(60 mg) \times cov(\theta_0, \theta_1)}$$

Where:

- $\overline{\Delta QTc_{60mg}}$  is the predicted  $\Delta QTc$  at 60 mg;
- $\theta_0$  is the estimated fixed intercept term;
- $\theta_1$  is the estimated fixed slope for concentrations;
- $t(0.95, DF)$  is the 95th quantile from the student distribution with  $DF$  degrees of freedom;
- SE is the standard error ;
- $var(\theta_0)$ ,  $var(\theta_1)$  and  $cov(\theta_0, \theta_1)$  are respectively the variance of  $\theta_0$  and  $\theta_1$  and their covariance.

The summary measure of the study is the geometric mean and 90% CI of the predicted  $\Delta QTc$  at 60 mg Cmax. If the upper bound of 90% CI for this predicted  $\Delta QTc$  falls below the 10 msec mark, the conclusion of the study is that there is no clinically relevant QTc prolongation up to and including the 60 mg dose. In case the upper 90% CI limit does not fall below the 10 msec mark, the same evaluation will be performed for the  $\Delta QTc$  at the geometric mean Cmax of the 40 mg once daily dose.

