#### 4.9.5 Sensitivity analyses

A sensitivity analysis will be performed to ensure that there is no bias in the calculated geometric mean of the Cmax at the 60 mg once daily dose, in case:

- Twenty percent (20%) or more of the total PK data is missing, or
- Twenty percent (20%) or more of participants (8 participants or more) at the 60 mg once daily dose have either missing paroxetine concentration data around the Cmax at the 60 mg dose level, or an intercurrent event of “any events affecting absorption within 1 hour of the dose” at the 60 mg dose

This analysis will consist of a population pharmacokinetic (PopPK) model-fitting of the individual paroxetine concentration data without the estimation of population level parameters (post-hoc or Bayesian fit), using a paroxetine popPK model developed internally at GSK. Appropriateness of the available paroxetine popPK model will be determined based on goodness-of-fit plots (e.g. population and individual prediction [PRED, IPRED] vs observed concentrations [DV], CWRES vs IPRED). A description of the popPK model, if used for sensitivity analysis, will be included in the study report.

The individual PK parameters from the Bayesian model fit will allow the model-based individualised prediction of the Cmax at the 60 mg once daily dose for those participants with missing data, based on the available paroxetine concentration data at the earlier doses. Through this method, a geometric mean of Cmax at the 60 mg dose can be calculated that should be less affected by dropout, missing data, or intercurrent events. An additional calculation of the upper limit of the 90% CI of  $\Delta QTc$  will then be performed using the Cmax of the 60 mg dose calculated using this method. In case the evaluation of  $\Delta QTc$  finds a  $\geq 10$  ms upper 90% CI limit at the 60 mg dose, the same model-based prediction of Cmax at the 40 mg dose for dropouts will be performed, where required. If such a sensitivity analysis is performed, results from both the regular analysis (without PK model fitting and predictions) and the sensitivity analysis will be presented in the study report.

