10. Vital signs, laboratory assessments (coagulation parameters, haematology with differential, clinical and liver chemistry, pregnancy test, and paroxetine concentrations samples) and ECG data will all be captured at visits on site. During the treatment period, all laboratory samples and vitals (including one paroxetine concentration sample) should be obtained pre-dose.
11. All ECGs will be performed in triplicate collected within 5 min at each timepoint. ECG triplicates will be performed once at Screening (Visit 1), and at Follow-Up Visit and at discontinuation or withdrawal visits. At Visits 2 (Day -1), 3 (Day 7), 4 (Day 14), and 5 (Day 21) ECG triplicates will be performed 15 min pre-dose (-0.25 h) and post-dose at the following timepoints 1, 2, 3, 4, 4.5, 5, 5.5, 6, 8, 10, 12h. Each ECG triplicate will be combined with paroxetine concentration assessment. Paroxetine concentrations at Visits 3 (Day 7), 4 (Day 14), and 5 (Day 21) will be procured at the following timepoints: -0.25, 1, 2, 3, 4, 4.5, 5, 5.5, 6, 8, 10, 12 h. One sample will be collected for paroxetine concentrations on Day -1 at 0.25h (pre-dose). The paroxetine dose should be taken at the same clock time each time, at a time approximately between 07:00-09:00 (7/10 am). When scheduled for the same time, ECGs should be performed before blood sampling to avoid impact on ECG parameters.
12. .
13. At Visits 2 (Day -1), 3 (Day 7), 4 (Day 14), and 5 (Day 21), follow-up visit and at discontinuation or withdrawal visits, serial ECG review will be performed by Mortara system
14. Negative urine pregnancy test result must be confirmed prior to dosing in female participants of reproductive potential. If a urine test cannot be confirmed as negative (e.g., an ambiguous result), a serum pregnancy test is required. In such cases, the participant must be excluded from participation if the serum pregnancy result is positive.
15. FSH test be performed for postmenopausal women only.
16. COVID-19 testing will be performed as per site practice.
17. Participants will be discharged from the clinic 3 hours after the morning dose on Study Days 1, 8, and 15 (Visit 2, 3, 4) to subsequently take paroxetine doses at home until the next visits in clinic.
18. Participants will get discharge on either Day 21 or Day 22 (may stay overnight) as per the convenience.

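### The SAP's decision value, theta0 + theta1 x Cmax(60 mg), names no level or weights for its 12-level time factor, so it is not fully defined and may include drug-free time-of-day change

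*SAP*

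**What the plan says.** **Protocol 9.3.2.2** models delta-QTc with an intercept theta0, a concentration slope theta1, one coefficient theta2 multiplying TIME, and a centred baseline term. In that form theta0 belongs to TIME = 0.

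**SAP 4.9.2** makes the time term a factor: theta2,k "is the fixed multilevel categorical effect associated with time factor". The code puts ATPTN in both CLASS and MODEL. The schedule in SAP 6.1 sets the levels: ECGs are taken "15 min pre-dose (-0.25 h) and post-dose at the following timepoints 1, 2, 3, 4, 4.5, 5, 5.5, 6, 8, 10, 12h", which is 12 times. The intercept is described only by saying that it "is the population mean intercept in the absence of a treatment effect".

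**The decision quantity** is theta0 + theta1 x Cmax(60 mg). In the code it is "ESTIMATE 'DDQTC_60MG' INT 1 PCSTRESN CMAX60MG /CL ALPHA=.1". In SAP 4.9.2.3, theta0 "is the estimated fixed intercept term", and the SE is built from var(theta0), var(theta1) and their covariance alone (the terms that "are respectively the variance of" the two parameters). Neither place gives a time level, weights or a constraint.

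**Where else it is used.** SAP 4.9.2.3 repeats the prediction at 40 mg: "In case the upper 90% CI limit does not fall below the 10 msec mark, the same evaluation will be performed for the" change at the 40 mg geometric mean Cmax. SAP 4.9.5 provides for "An additional calculation of the upper limit of the 90% CI of" delta-QTc with a model-based Cmax.

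**Baseline and drug-free data.** For the primary analysis, baseline is the single Day -1 collection at -0.25 h (SAP 4.9.1). Day -1 records after baseline enter the model with concentration 0 (SAP 4.9.2). There is no placebo arm.

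**Change log.** SAP 4.17 lists only the new definition of the Enrolled set.

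**The concern.** One number decides the study. If its upper 90% limit is below 10 msec, the plan concludes that there is no clinically relevant prolongation up to 60 mg. A model with an intercept and a full set of time levels does not fix theta0 until a reference level or a weighting is named, and the plan names none.

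The choice can matter because change is measured from one early-morning value. At any later time, delta-QTc contains the drug effect plus whatever QTc does by itself between the pre-dose reading and that time. A natural fall would hide part of a drug effect. A natural rise would add to it. SAP 4.9.2.1 itself treats diurnal variation as possible.

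**Working it through.** The plan gives no value for the time-of-day change or for the time level of the prediction, so there is no stated figure to reproduce. The check is of estimability first, then of what each possible reading estimates.

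**1. Estimability.** Inputs: 36 participants (SAP 4.16); 11 Day -1 records each at concentration 0 (the 12 scheduled times less baseline); 12 records on each of Days 7, 14 and 21.
- Rows: 36 x (11 + 3 x 12) = 1,692.
- Fixed-effect columns: intercept 1 + baseline 1 + time 12 + concentration 1 = 15.
- Rank: 14, because the 12 time columns add up to the intercept column.
- An estimable contrast must therefore have time coefficients that sum to its intercept coefficient. With intercept 1 and time coefficients all 0, the sums are 1 and 0, so the contrast is not estimable.
- Full weight on one time level, weights of 1/12 each, and the slope-only contrast theta1 x Cmax are all estimable.

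**2. What each reading estimates.** Let g(k) be the drug-free change in QTc from -0.25 h to time k, so g(-0.25) = 0. With time weights w(k) that sum to 1, the expected value is

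theta1 x Cmax + sum of w(k) x g(k).

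Only full weight on -0.25 h removes the second term for every possible curve.

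**3. Size under an assumed drift.** Assume a linear drug-free drift of S msec from -0.25 h to 12 h, so g(k) = S x (t + 0.25)/12.25.
- Equal weights: the 12 times sum to 60.75, and (60.75 + 12 x 0.25)/(12 x 12.25) = 0.434, so the shift is 0.43 x S.
- 5 h: 5.25/12.25 = 0.429, so 0.43 x S.
- 12 h: 12.25/12.25 = 1, so 1.0 x S.
- -0.25 h: 0.
- Protocol form (theta0 at TIME = 0): 0.25/12.25 = 0.02, about 0.1 msec for S = 5.

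Example with an assumed true effect of 10 msec at 60 mg and S = -5. The 40 mg column assumes 0.6 of the 60 mg concentration, so a true effect of 6.

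| Reading | 60 mg (msec) | 40 mg (msec) |
|---|---|---|
| -0.25 h level | 10.0 | 6.0 |
| Equal weights | 7.83 | 3.83 |
| 5 h level | 7.86 | 3.86 |
| 12 h level | 5.0 | 1.0 |
| theta1 x Cmax | 10.0 | 6.0 |

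Noise-free fits of the SAP's fixed-effect model return the same values for assumed pre-dose/peak ratios of 0.4 to 0.8 and Cmax log-SDs of 0.3 to 0.7.

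**4. Code against formula.** If the software filled the missing ATPTN coefficients with equal weights, the code would return the equal-weight row. If its solution table set the 12 h level to zero, theta0 and var(theta0) taken from that table would give the 12 h row. In the example that is 7.83 against 5.0 from one fit. SAS was not run, so these conventions are assumptions. The point is that the plan states neither.

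**5. Effect on the decision (simulation).** Assumptions: n = 36, random intercept SD 5.5, residual SD 5, cosine drug-free curve, 200 runs per scenario. Entries are the probability that the upper limit is at least 10 msec.

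| Scenario | -0.25 h | 5 h | 12 h | Equal weights |
|---|---|---|---|---|
| True effect about 5, flat curve | 0.5% | 0.5% | 0.5% | 0.5% |
| True effect about 5, rising curve, 5 msec peak to trough | 0.5% | 49% | 71% | 31% |
| True effect about 10, falling curve, 10 msec peak to trough | 95.5% | 0% | 0% | 0% |

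Mean SEs were 1.05 (-0.25 h), 1.02 (5 h), 1.03 (12 h) and 0.95 (equal weights). The pre-dose level is slightly less precise because it has no drug-free rows, against 36 at each other time.

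**The case against.** **The code is printed and the software is named.** A reader might infer that two analysts running the SAP code would report different numbers. The documents do not support that: the same code on the same data should give the same output, either a number or a non-estimable flag. What stands is that the plan does not say what that output means, and that the formula in SAP 4.9.2.3 need not agree with it.

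**The choice cannot simply be made after the data are seen.** SAP 1 has the plan finalised before database lock and later changes recorded in a modification form. Adding time weights to the code would be such a change. An undocumented choice could enter only through the formula, which leaves the level open.

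**The declared measure is model-predicted change from baseline.** A reader might infer, helped by the code label DDQTC_60MG, that the plan intends a placebo-corrected or same-time contrast and that theta1 x Cmax must replace the primary measure. Protocol 1.1, 3 and 9.3.2.2 and SAP 2.1 do not say this. In a single-arm study, drug-free change can be part of the declared quantity. That objection stands against replacing the estimand. It does not remove the need to say at which time the prediction is made.

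**The SAP looks at time trends.** It inspects Day -1 and allows a (co)sine form, which would remove the 12-level rank problem. That step is optional, and the prediction would still need a stated time.

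**There is a natural reference.** SAP 4.9.2 labels baseline as time 0, and the protocol ties theta0 to TIME = 0. This makes the intended level plausible, but the SAP does not state it for the prediction.

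**Conclusion.** The point holds. The SAP changed the form of the time term without adapting the prediction, and SAP 4.17 does not record the change. Read literally, with zero time coefficients, the code's contrast is not estimable. The formula depends on an unstated reference level, and the two need not agree. This is established from the documents and the rank check, with no assumption about QTc.

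The numerical effect is conditional. It would go too far to say that the result is biased by a given amount, or in a given direction: the documents give no drug-free curve, and with a flat one every reading agrees. Under an assumed linear drift, the shift is 0.43 x S (equal weights or 5 h) or 1.0 x S (12 h); for S = 5 that is about 2.2, 2.1 and 5.0 msec respectively, against a 10 msec threshold. Shifts of that size could change the conclusion either way, so this should be settled before database lock.

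**What to change.** Before database lock:

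1. **Code.** Add explicit ATPTN coefficients to the ESTIMATE line, with 1 on the -0.25 h level and 0 on the other eleven, and state the level order. This agrees with the protocol's theta0 at TIME = 0, apart from the quarter hour.
2. **Formula and SE.** In SAP 4.9.2.3, add theta2 at -0.25 h to the prediction and its variance and covariances to the SE. Equivalently, declare theta2 at -0.25 h to be zero; the printed formula and SE are then complete. If a (co)sine form is used instead, state the same prediction time.
3. **Carry-over.** Use the same form for the 40 mg evaluation and for the Cmax sensitivity analysis in SAP 4.9.5.
4. **Record.** List the move from a single TIME coefficient to a time factor in SAP 4.17.
5. **Supporting result.** Report theta1 x Cmax, the contrast with concentration 0 at the same time point, with 90% CI Cmax x (theta1 +/- t x SE(theta1)). Making it the primary measure is an optional estimand choice for the sponsor and would need the wording in SAP 2.1 and Protocol 1.1, 3 and 9.3.2.2 changed.

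**Cost.** One code line, one formula with its SE, and one entry in SAP 4.17; no new data. The SE may be slightly larger at -0.25 h.

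**Limit.** No version removes drift between Day -1 and Days 7 to 21. With assumed concentration ratios of 0.25/0.6/1 across the doses and the PK ranges above, a 1 msec step on Days 7 to 21 adds roughly 1.1 to 1.6 msec at -0.25 h, 0.9 to 1.3 with equal weights and 0.3 to 0.8 to theta1 x Cmax. That is a further reason to report the last one alongside.

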#### 4.9.2.1 Underlying assumptions

##### Effect on HR

Time course of mean changes in HR will be displayed by dose as detailed in Section 4.12.5.

##### Appropriateness of the QT correction off-drug (QTc is independent of HR):

In healthy participants, Fridericia correction of the QT interval (QTcF) is usually considered appropriate for drugs with limited effects on HR. QTcF is computed as  $QTcF$  (msec) =  $QT/(RR/1000)^{1/3}$ .

The appropriateness of the correction can be assessed by determining if the QTc is independent of the HR using drug free data. For that purpose, a scatter plot of QTcF values (y-axis) versus HR values (x-axis) obtained at Visit 2 (Day -1) will be provided with linear and non-linear (loess) regression lines to assess the lack of relationship between QTcF and HR off-drug. Moreover, similarity of the range of HR off- and on-drug, to support the correction in both cases, will be assessed by plotting the mean QTcF values calculated by decile of HR for each visit (off-drug on Visit 2 and on-drug on Visit 3, 4 and 5). Linear mixed effects lines and 95% confidence intervals computed for each visit will be plotted on the same graph.

##### Appropriateness of the QT correction on-drug:

In addition, the potential of paroxetine to significantly increase or decrease HR should be evaluated. Mean increase or decrease  $> 10$  beats/min are considered sufficient to impact the quality of the Fridericia correction and the primary endpoint assessment. The impact of paroxetine on HR will be

assessed from the graphical display of change from baseline in HR ( $\Delta$ HR) described in Safety Evaluation (Section 4.12.5).

If these graphical explorations suggest insufficient HR correction of the QT interval, alternative corrections, such as Bazett (QTcB (msec) = QT/(RR/1000)1/2), could be evaluated.

**No time delay between drug concentration and effect on QTc (direct effect hypothesis, no PK/PD hysteresis):**

The direct temporal relationship between paroxetine concentrations and  $\Delta$ QTcF will be assessed graphically by plotting the time course of mean  $\Delta$ QTcF with the time course of paroxetine concentrations geometric mean by visit. If for the two highest doses of paroxetine (Visits 4 and 5) a delay (hysteresis) between the time to reach the peak concentration and the peak QTc effect is more than 1 hour, other modeling strategy may be explored.

**Linear relationship between paroxetine relationship and  $\Delta$ QTcF**

The linear relationship will be assessed using a scatter plot of  $\Delta$ QTcF (y-axis) vs. concentrations (x-axis), with linear and non-linear (loess) trend lines. The trend lines, directly obtained from the SAS® graphical procedures, will not reflect the model fit of the data but rather rough fixed regressions (without random effects) to detect drug effect and whether there are major violations to the linear assumption (in case of drug effect)

In case of the linearity assumption cannot be accepted, alternative models will be explored. A non-linear alternative could be, for example, the Emax model for which the linear component  $((\theta_1 + \eta_{1,i}) * C_{i,k})$  is replaced by a component of the form  $(\theta_{1,1} + \eta_{1,i}) * C_{ik}^\gamma / (\theta_{1,2}^\gamma + C_{ik}^\gamma)$ , where  $\theta_{1,1}$  is the maximal asymptotic increase from  $\theta_0$ ,  $\theta_{1,2}$  is the concentration at which the effect is half  $\theta_{1,1}$ ,  $\gamma$  is the hill coefficient and  $\eta_{1,i}$  is the random effect associated with  $\theta_{1,1}$ .

As such an example for a full nonlinear model could be written as :

$$\Delta QTc_{i,k} = (\theta_0 + \eta_{0,i}) + (\theta_{1,1} + \eta_{1,i}) * \frac{C_{ik}^\gamma}{\theta_{1,2}^\gamma + C_{ik}^\gamma} + \theta_{2,k} * TIME_{i,k} + \theta_3 (QTc_{i,k=0} - \overline{QTc_0}) + \varepsilon_{i,k}$$

The model parameters will be estimated including the precision around the parameter estimates using a maximum likelihood approach. Initial values will be determined from the graphical display.

